7.6 Multiple Comparisons/Multiplicity

The following stepwise process will be conducted for testing the secondary efficacy endpoints in order to control for multiplicity. These tests will be performed for only the intent-to-treat (ITT) population. The testing process will terminate whenever a statistical test for a step is not significant. All subsequent tests for the remaining steps will be considered not significant. The order of testing is percent change in inflammatory lesion count from Baseline to Week 12, percent change in non-inflammatory lesion count from Baseline to Week 12 and the proportion of subjects who are dichotomized to success (minimum 2-grade improvement from Baseline).

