A total of 420 adult subjects were randomized to active and vehicle in a 2:2:2:1:1 fashion. Study treatments continued for 12 weeks. Subjects returned to the study clinic at Weeks 1, 2 (phone call only), 4, 8 and 12 (study exit).

The results of the study showed that all three Olumacostat Glasaretil Gel treatment groups demonstrated statistically significantly greater reductions in the absolute change in inflammatory lesion counts from baseline to Week 12 than the combined vehicle group. The LS mean changes in inflammatory lesion counts were -14.6 and -14.5, and -15.0 for the Olumacostat Glasaretil Gel, 4.0% QD, 7.5% QD, and 7.5% BID groups, respectively, compared with -10.7 for the combined vehicle QD group (P = 0.011, P = 0.014, and P = 0.011 respectively). All 3 Olumacostat Glasaretil Gel treatment groups showed statistically significantly greater reductions in the absolute change in noninflammatory lesion counts from baseline to Week 12 than the combined vehicle group. The LS mean changes in noninflammatory lesion counts at Week 12 were -15.3, -13.4, and -17.5 for the DRM01B Olumacostat Glasaretil Gel 4.0% QD, 7.5% QD, and 7.5% BID groups, respectively, compared with -9.3 for the combined vehicle group (P = 0.004, P = 0.050, and P < 0.011 respectively).

The Olumacostat Glasaretil Gel 4.0% QD and 7.5% BID groups each had a statistically significantly greater proportion of subjects achieve a minimum 2-grade improvement (reduction) in IGA score from baseline at Week 12 compared with the combined vehicle group. The percent of subjects achieving this endpoint was 21.6% in the Olumacostat Glasaretil Gel 4.0% QD and 25.9% of subjects in the Olumacostat Glasaretil Gel 7.5% BID group (compared with 9.8% in the combined vehicle QD group (P = 0.024 and P = 0.004, respectively).

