11.4 Secondary Efficacy

The percent change from baseline to Week 12 in inflammatory and non-inflammatory lesion counts will be analyzed using the same ANCOVA method described for the primary endpoint.

The proportion of subjects who are dichotomized to success (minimum 2-grade improvement from baseline) at Week 12 will be analyzed using the same logistic analysis method described for the primary endpoint.

The following stepwise process will be conducted for testing the secondary efficacy endpoints in order to control for multiplicity. These tests will be performed for only the ITT population. The testing process will terminate whenever a statistical test for a step is not significant. All subsequent tests for the remaining steps will be considered not significant. The order of testing is percent change in inflammatory lesion count from baseline to Week 12, percent change in non-inflammatory lesion count from baseline to Week 12, and the proportion of subjects who are dichotomized to success (minimum 2-grade improvement from baseline).

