4.2 Determination of Sample Size

The sample size for this study was based on estimates from the DRM01B-ACN02 study observed Week 12 results. Estimates were combined for all three active treatment groups as well as for the two vehicle groups. All power calculations were performed with nQuery Advisor Version 7.0 for a two-sided test at alpha = 0.05.

For inflammatory lesion change a sample size of 300 Olumacostat Glasaretil Gel and 150 Olumacostat Glasaretil Gel, Vehicle subjects has at least 95% power to detect a statistically significant difference with a significance level of 0.05 using the estimated absolute change from Baseline in treatment means of -15.21 and -9.7 for Olumacostat Glasaretil Gel versus its vehicle, respectively, with a standard deviation (SD) of 11.00.

For non-inflammatory lesion change a sample size of 450 Olumacostat Glasaretil Gel and 225 Olumacostat Glasaretil Gel, Vehicle subjects has 95% power to detect a statistically significant difference with a significance level of 0.05 using the estimated absolute change from Baseline in treatment means of -14.73 and -9.70 for Olumacostat Glasaretil Gel versus its vehicle, respectively, with a SD of 16.72.

The success rate for dichotomized IGA is estimated to be 20.5% in the Olumacostat Glasaretil Gel subjects and 9.6% in vehicle subjects. A sample size of 444 Olumacostat Glasaretil Gel and 222 Olumacostat Glasaretil Gel, Vehicle will have 95% power to detect a statistically significant difference in proportions of successes. These calculations were performed with nQuery Advisor Version 7.0 for a two-sided continuity corrected chi-square test at alpha = 0.05.

To allow for a slight loss in power due to dropouts and withdrawals as well as to accommodate sufficient power in all three co-primary variables, a sample of 700 subjects randomized to 2 to 1 for Olumacostat Glasaretil Gel (n=467) and vehicle (n=233), respectively, will be enrolled in the trial.

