7. STATISTICAL METHODS AND ANALYSIS

7.1 General Methodology

All analyses will be performed using SAS® Version 9.3 or later. No interim analyses are planned. Except where noted, all statistical tests will be two-sided and will be performed at the 0.05 level of significance.

Descriptive statistics will be used to provide an overview of the efficacy and safety results. For categorical parameters, the number and percentage of subjects in each category will be presented. For continuous parameters, descriptive statistics will include n (number of observations), mean, SD, median, minimum and maximum. Appropriate inferential statistics will be used for the primary, secondary and exploratory efficacy variables.

The primary method of handling missing efficacy data will be the method of Markov Chain Monte Carlo (MCMC) multiple imputation.

The primary method of dichotomizing the IGA score will be to consider a subject a "success" if the IGA at a post-baseline visit is 0 or 1 and 2 or more grades lower than at Baseline; otherwise the subject will be considered a treatment "failure".

Reported AEs, medical history terms, prior and concomitant procedures and therapies and washout procedures will be classified on the basis of Medical Dictionary for Regulatory Activities (MedDRA) terminology, Version 19.1. Prior and concomitant medications and washout medications will be classified on the basis of World Health Organization Drug Dictionary (WHO-DDE) terminology, Format B2, Version March 1, 2016.

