7.7 Examination of Subgroups

Subset analyses will be conducted for the ITT population for subgroups based on the following:

- Baseline IGA;
 - O Categorized as Baseline IGA = 3 (Moderate) and Baseline IGA = 4 (Severe); due to the inclusion criteria requiring subjects to have either a 3 or 4 IGA score at study entry other IGA response categories will not be presented;
- Gender:
- Age:
 - O Dichotomized as less than the median age of ITT subjects and greater than or equal to the median age of ITT subjects;
 - O Categorized as less than 18, 18 to less than the median age of ITT subjects and greater than or equal to the median age of ITT subjects; If the median age of ITT subjects is less than 18 then the subgroup will be <18 and >= 18
- Ethnicity;
- Race:
 - O Categorized as White and Non-White; subjects indicating more than one race category which includes both white and a non-white race will be summarized under the Non-White subgroup.
- Oral Contraceptives Approved for the Treatment of Acne:
 - Categorized as Oral Contraceptives Approved for Acne Treatment Usage and No Oral Contraceptives Approved for Acne Treatment Usage. All male subjects will be grouped into the No Oral Contraceptives Approved for Acne Treatment Usage category.

Subset analyses will be conducted on the variables absolute change from Baseline in inflammatory lesions and non-inflammatory lesions at Week 12 as well as the dichotomized IGA score at Week 12. These analyses will contain descriptive statistics only.

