7.9.7.2 Secondary Efficacy Analyses

The percent change from Baseline to Week 12 in inflammatory and non-inflammatory lesion counts will be analyzed using the same ANCOVA method described for the primary endpoint.

The proportion of subjects who are dichotomized to success (minimum 2-grade improvement from Baseline) at Week 12 will be analyzed using the same logistic analysis method described

for the primary endpoint. A stepwise process will be conducted for testing the secondary efficacy endpoints in order to control for multiplicity, refer to Section 7.6 for details.

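### The secondary testing chain is not conditional on the three co-primary endpoints, so a secondary can be declared significant at two-sided 0.05 after a co-primary fails

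*SAP*

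**What the plan says.** The multiplicity section, SAP 7.6, opens: "The following stepwise process will be conducted for testing the secondary efficacy endpoints in order to control for multiplicity". The tests are restricted to the ITT population. The order is percent change in inflammatory lesions, percent change in non-inflammatory lesions, then at least a 2-grade IGA improvement. Protocol 11.4 gives the same order and the same stopping rule: "The testing process will terminate whenever a statistical test for a step is not significant". No co-primary is a step in the chain.

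The other places where a condition could sit do not contain one:

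- SAP 7.9.7.2 only points back: "A stepwise process will be conducted for testing the secondary efficacy endpoints in order to control for multiplicity, refer to Section 7.6 for details".
- Protocol 11.3 and SAP 7.9.7.1, on the primary analyses, give models and no success rule.
- SAP 7.1 states that, except where noted, "all statistical tests will be two-sided and will be performed at the 0.05 level of significance".
- SAP 5, which lists departures from the protocol, does not touch the chain.

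The term co-primary appears only in the sample-size text (Protocol 11.14, SAP 4.2), where 700 subjects are chosen partly to "accommodate sufficient power in all three co-primary variables".

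**The concern.** In a confirmatory trial, a secondary claim is normally available only after the primary objective is met. Here a literal reader would run the chain whatever the co-primaries show and call its results significant at 0.05.

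The secondaries are close relatives of the primaries. Percent change re-expresses the absolute change in the same lesion count. The 2-grade IGA endpoint contains the IGA co-primary. Protocol 5.3.1 requires IGA of at least 3 on a 0 to 4 scale. From grade 3, a 2-grade improvement means reaching 0 or 1, which is the primary success itself. From grade 4 it also admits grade 2. The two endpoints therefore differ only for grade-4 subjects who reach exactly grade 2. A trial that failed the IGA co-primary could still declare this looser form significant, provided both percent-change lesion tests pass.

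What is at stake is error control across the primary claim and the secondaries together, and a decision rule that cannot be settled credibly once results are known.

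**Working it through.** **1. The plan's own figures (SAP 4.2).** All three reproduce.

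- Inflammatory, 300/150: z = 5.51 / (11.00 × √(1/300 + 1/150)) = 5.01; power = Φ(5.01 − 1.96) = 99.9%. The plan says at least 95%.
- Non-inflammatory, 450/225: z = 5.03 / (16.72 × √(1/450 + 1/225)) = 3.68; power = Φ(3.68 − 1.96) = 95.8%. The plan says 95%.
- IGA, 20.5% v 9.6%, continuity-corrected chi-square, 2:1: 222 vehicle subjects for 95% power, an exact match.

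The documents state no error rate across primary and secondary endpoints, so there is no figure of that kind to reproduce.

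**2. One co-primary and its paired secondary null, everything else strong.** Assume all three co-primaries are required. The other two then pass almost surely, and so do the other steps of the chain. A false statement is made if either null test is significant:

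error = P(|Z₁| > 1.96 or |Z₂| > 1.96), with Z₁ and Z₂ bivariate normal with correlation r.

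| assumed r | two-sided error | favouring active only |
|---|---|---|
| 0.99 | 0.0566 | 0.0283 |
| 0.95 | 0.0646 | 0.0323 |
| 0.90 | 0.0704 | 0.0352 |
| 0.79 | 0.0787 | 0.0393 |
| any r, with a gate | 0.050 | 0.025 |

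The one-direction column is half the two-sided column.

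**3. Why that range of r.** The documents give no correlation, so these are illustrations.

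- IGA pair: for nested binary endpoints with rates pA (strict) and pB (relaxed), r = √[pA(1 − pB) / (pB(1 − pA))]. Taking 9.6% as an assumed strict rate and adding an assumed 1 point gives √(0.096 × 0.894 / (0.106 × 0.904)) = 0.946 and error 6.5%. Adding 5 points gives √(0.096 × 0.854 / (0.146 × 0.904)) = 0.788 and error 7.9%.
- Lesion pairs: simulated absolute-change and percent-change ANCOVA statistics at 467/233 (baseline at least 20, assumed mean 28 to 45 and SD 7 to 25, change SD about 11) correlate 0.85 to 0.98, giving error 5.9% to 7.5%.

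**4. All six tests, chain order respected.** Simulation with null mean 0, strong mean 6, pair correlation 0.79, 0.90 or 0.99, and cross-endpoint correlation 0, 0.5 or 0.7:

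| null pairs | error as written |
|---|---|
| one (whichever it is) | 0.0563 to 0.0790 |
| two | 0.0501 to 0.0587 |
| all three | 0.0500 to 0.0544 |

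With a gate the error is 0.050 when one pair is null, and no higher in the other rows. As more pairs become null, a false all-three success becomes rare and the total falls towards the chain's own 5%.

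**5. How often the rule would be needed (not an error rate).** At 467/233 with the planned effects, the co-primary powers are above 99.9%, 96.3% and 96.0%. If they are independent, at least one fails in 1 − (0.99999 × 0.9633 × 0.9596) = 7.6% of trials. That uses the continuity-corrected sizing test for IGA; without the correction it is 6.7%. Under the planned effects, the IGA co-primary fails and the 2-grade endpoint is then reached and significant in 0.6% or 0.9% of simulated trials, for an assumed 1 or 5 added points.

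**The case against.** The strongest reply is that this is an omission, not a permission. Neither document says a secondary may be claimed after a co-primary fails. The endpoints are ranked primary and secondary, and the trial is sized for all three co-primaries, so the intended hierarchy is readable. The chain also does what it literally claims: it covers the secondary family, and fixed-sequence testing controls error there at 0.05. The standard across both families is one this review applies; the plan does not state it. All of that stands, and it limits the weight of the point. It does not supply the missing rule. Ranking endpoints does not say what happens to the chain when a co-primary fails.

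Three stronger readings are tempting but unsupported.

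- A reader might infer that error nearly doubles, to 9.75% or a bound of 10%. The 9.75% requires the null co-primary and its secondary to be independent. That is implausible for two expressions of the same lesion count, or for nested IGA definitions.
- A reader might derive the IGA correlation from two vehicle rates: 9.8% for 2-grade improvement in Protocol 1.2 ("compared with 9.8% in the combined vehicle QD group") and 9.6% in SAP 4.2 ("The success rate for dichotomized IGA is estimated to be 20.5% in the Olumacostat Glasaretil Gel subjects and 9.6% in vehicle subjects"). The documents do not show that these are the relaxed and strict rates on the same data. The 2-grade rates in Protocol 1.2 are 21.6% and 25.9% in two of three equally allocated active arms. A pooled 20.5% would then need 3 × 20.5 − 21.6 − 25.9 = 14.0% in the third arm, the one not reported as significant on that endpoint. The sample-size text may therefore be quoting the relaxed endpoint, and the pair cannot be used.
- A reader might take the 6.7% to 7.6% chance of a failed co-primary as false claims. It is not an error rate, because the effects are real in that scenario.

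**Conclusion.** The gap is real and modest. As written, the plan allows a secondary to be declared significant at two-sided 0.05 after a co-primary fails, and it does not control error across the primary and secondary claims.

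In the worst coherent case, two-sided error is about 5.7% to 7.9% against 5.0% with a gate (2.8% to 3.9% against 2.5% counting only claims favouring active). This rests on three assumptions: all three co-primaries are required, exactly one pair is null with the rest strong, and correlations lie between 0.79 and 0.99. In other null configurations the excess over 5% is under one percentage point.

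The primary claim is not affected: adding secondary tests does not change the three primary tests. Nor do the documents show any intention to claim secondaries from a failed trial. They only fail to rule it out.

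**What to change.** Add the following to SAP 7.6 and Protocol 11.4, before unblinding:

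1. The study succeeds only if all three co-primary tests are significant at two-sided 0.05 in the ITT population.
2. The stepwise secondary tests are confirmatory only if (1) holds; otherwise secondary p-values are nominal.

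Sentence (1) closes a separate small omission. The all-three rule is nowhere stated, and SAP 7.9.7 presents efficacy in both the ITT and PP populations, so the population for the primary decision should be named. Sentence (2) is the gate, and the error figures above measure its effect alone.

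Sample size, primary tests and power do not change. The cost is that no secondary can be claimed as confirmatory when a co-primary fails. If the sponsor already intends this, writing it down costs nothing further.

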7.7 Examination of Subgroups

Subset analyses will be conducted for the ITT population for subgroups based on the following:

- Baseline IGA;
 - O Categorized as Baseline IGA = 3 (Moderate) and Baseline IGA = 4 (Severe); due to the inclusion criteria requiring subjects to have either a 3 or 4 IGA score at study entry other IGA response categories will not be presented;
- Gender:
- Age:
 - O Dichotomized as less than the median age of ITT subjects and greater than or equal to the median age of ITT subjects;
 - O Categorized as less than 18, 18 to less than the median age of ITT subjects and greater than or equal to the median age of ITT subjects; If the median age of ITT subjects is less than 18 then the subgroup will be <18 and >= 18
- Ethnicity;
- Race:
 - O Categorized as White and Non-White; subjects indicating more than one race category which includes both white and a non-white race will be summarized under the Non-White subgroup.
- Oral Contraceptives Approved for the Treatment of Acne:
 - Categorized as Oral Contraceptives Approved for Acne Treatment Usage and No Oral Contraceptives Approved for Acne Treatment Usage. All male subjects will be grouped into the No Oral Contraceptives Approved for Acne Treatment Usage category.

Subset analyses will be conducted on the variables absolute change from Baseline in inflammatory lesions and non-inflammatory lesions at Week 12 as well as the dichotomized IGA score at Week 12. These analyses will contain descriptive statistics only.

7.8 Analysis Populations

7.8.1 Randomized Population

All subjects who are randomized to study treatment will be included in the randomized population and will be analyzed according to the treatment group they were randomized.

7.8.2 Intent-to-Treat (ITT) Population

All subjects in the randomized population who are dispensed study drug will be included in the ITT population and will be analyzed according to the treatment group they were randomized. All efficacy analyses will be presented using the ITT population.

7.8.3 Safety Population

All subjects in the randomized population who receive at least one confirmed dose of study drug and have at least one post-baseline safety assessment will be included in the safety population and will be analyzed according to the treatment they received. All safety analyses will be performed using the safety population.

7.8.4 Per-Protocol (PP) Population

All subjects in the safety population who complete the Week 12 evaluation without any significant protocol violations will be included in the PP population and analyzed according to the treatment group they were randomized. The PP population will include subjects in the safety population who do not meet any of the following criteria:

- Violated the inclusion/exclusion criteria;
- Have taken any interfering concomitant medication;
- Did not attend the Week 12 visit:
- Have missed both the Week 4 and Week 8 study visits;
- Have not been compliant with the dosing regimen (i.e. subjects must apply 80-120% of the expected applications of study medication during participation in the study);
- Out of visit window at the Week 12 visit by ± 5 days.

Subjects that discontinue treatment or from the study due to an AE related to study treatment or documented lack of treatment effect will be included in the PP population. Prior to breaking the

blind, other additional criteria may be added to the list to accommodate for unforeseen events that occurred during the conduct of the trial that result in noteworthy study protocol violations.

All efficacy analyses will be performed on the PP population.

7.9 Statistical Analysis

All analyses will be performed by QST. All summary tables and data listings will be prepared utilizing SAS® software. The standard operating procedures of QST will be followed in the creation and quality control of all data displays and analyses.

All data collected at scheduled time points will be summarized, regardless of treatment with study drug. Post-treatment assessments for subjects who discontinue treatment but continued to be followed in the study will be included in summaries.

7.9.1 Baseline Definition

Baseline is defined as the last non-missing assessment prior to the first dose of study drug.

7.9.2 Visit Windowing

Data will be summarized based on nominal visit indications with the exception of data captured at early termination and unscheduled visits. Data from early termination and unscheduled visits will be summarized based on mapped visit values. The analysis windows for early termination and unscheduled visits are presented in the following table.

Scheduled Visit	Target Study Day	Window (Days)
Week 1	8	5 to 18
Week 4	29	19 to 42
Week 8	57	43 to 70
Week 12	85	71 to 98

Analysis Windows for Efficacy and Safety Assessments

Data collected at early termination and unscheduled visits prior to study day 5 will not be analyzed, with the exception of those identified as baseline values. Data collected at early termination and unscheduled visits after study day 98 will not be included in analyses.

The definition for the study day included in each study window is defined as below:

Study Day Prior to Day 1 = Visit Date – Day 1 Date

Study Day On or After Day 1 = Visit Date - Day 1 Date + 1.

If an assessment's mapped visit is a visit at which the subject has data from a scheduled visit present, or if no analyses are planned for the assessment at the mapped visit, the data collected at the early termination or unscheduled visit will not be included in analyses.

In the event of multiple values from unscheduled or early termination assessments within an analysis window, the value closest to the scheduled visit target study day will be used for analyses. If two values tie as closest to the time point (for example, one value is before and the other value is after the time point), then the later value will be selected.

Data collected at all visits will be included in the data listings with visit presented as reported by the site.

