8.8 Unscheduled Visits

Additional visits may be scheduled as necessary to ensure the safety and well-being of subjects who experience AEs. Laboratory evaluations, if necessary, will be collected and analyzed using the central laboratory for this study. Data will be recorded in the eCRF.

9 DETAILS OF ASSESSMENTS

Parental assistance for study drug application and study conduct procedures may be needed for younger subjects qualifying for study participation.

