7.9.8.3 Clinical Laboratory Evaluations

Laboratory test results will be summarized descriptively at Baseline and Week 12. Additionally, shifts from Baseline to Week 12 in laboratory test results based on normal ranges will be summarized with descriptive statistics. Individual laboratory test results will be presented in a by-subject listing.

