7.9.8.4 Local Skin Reactions

LSRs include erythema, peeling, dryness, burning/stinging and pruritus. These will be scored as 0 (None), 1 (Mild), 2 (Moderate) or 3 (Severe). LSRs will be summarized by treatment group and visit using descriptive statistics. Each subject's worst post-baseline grade for each LSR will also by summarized. Additionally, the number of subjects who experience mild, moderate or severe LSRs post-baseline will be presented overall, and by visit. By-subject listing of all LSRs, as well as subjects with any severe LSRs will be included.

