7.9.8.5 Other Observations Related to Safety

7.9.8.5.1 ECG Measurements

Descriptive statistics by treatment group and visit will be provided for the following ECG parameters: heart rate (HR), PR duration, RR duration, QRS duration, QT duration, QT interval corrected for heart rate using Bazett's formula (QTcB) and QT interval corrected for heart rate using Fridericia's formula (QTcF). Change from Baseline in ECG abnormalities will be summarized using shift tables at the Week 12 visit. Shift tables will be based on the following categories:

- PR Interval: < 100 msec, 100 220 msec and > 220 msec;
- QRS Interval: < 50 msec, 50 110 msec and > 110 msec;
- QTcF Interval: < 450 msec, 450 500 msec and > 500 msec.

The following treatment-emergent ECG abnormalities will be summarized for subjects in the safety population with at least one post-application ECG:

- PR Interval
 - \circ > 220 msec;
 - o > 220 msec and Change from Baseline > 25%;
- QRS Interval
 - \circ > 110 msec;
 - \circ > 110 msec and Change from Baseline > 25%;
- QTcF Interval
 - \circ > 450 480 msec;
 - 0 > 480 500 msec;
 - \circ > 500 msec;
 - o Change from Baseline > 30 60 msec;
 - o Change from Baseline > 60 msec;
 - \circ > 450 480 msec and Change from Baseline > 30 60 msec;
 - o > 450 480 msec and Change from Baseline > 60 msec;
 - \circ > 480 500 msec and Change from Baseline > 30 60 msec;
 - \circ > 480 500 msec and Change from Baseline > 60 msec;
 - > 500 msec and Change from Baseline > 30 60 msec;
 - > 500 msec and Change from Baseline > 60 msec.

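### The SAP 7.9.2 visit mapping drops early-termination ECGs and laboratory values before day 71 from the Week 12 tables, and conflicts with the worst-grade skin reaction and treatment-emergent ECG tables

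*SAP*

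**What the plan says.** SAP 7.9.2 sets analysis windows for efficacy and safety assessments: days 5 to 18 (Week 1), 19 to 42 (Week 4), 43 to 70 (Week 8) and 71 to 98 (Week 12). Scheduled visits keep their nominal label. For the rest the default is inclusion: "Data from early termination and unscheduled visits will be summarized based on mapped visit values". Exclusions follow:

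- "Data collected at early termination and unscheduled visits prior to study day 5 will not be analyzed", apart from values that serve as baseline.
- "Data collected at early termination and unscheduled visits after study day 98 will not be included in analyses".
- If the mapped visit already has scheduled data for the subject, or no analysis of the assessment is planned at that visit, "the data collected at the early termination or unscheduled visit will not be included in analyses".
- If several ET or unscheduled values share a window, only the one nearest the target day is used.

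All visits go to the data listings.

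The safety sections then define the tables. For laboratory tests (SAP 7.9.8.3), "shifts from Baseline to Week 12 in laboratory test results based on normal ranges will be summarized". ECG shift tables are at Week 12, while treatment-emergent ECG abnormalities (SAP 7.9.8.5.1) "will be summarized for subjects in the safety population with at least one post-application ECG". For LSRs (SAP 7.9.8.4), "Each subject's worst post-baseline grade for each LSR will also by summarized", and severity counts are given overall as well as by visit.

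Protocol 8.7 and Appendix 1 plan post-dose laboratory tests and ECGs only at the Week 12 or ET visit. Protocol 8.8 explains why off-schedule visits occur: "Additional visits may be scheduled as necessary to ensure the safety and well-being of subjects who experience AEs".

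**The concern.** A one-value-per-window rule suits a by-visit table, where each subject should count once per visit. It does not suit a table meant to show the worst value a subject reached, or whether an abnormality ever appeared after dosing. The readings it discards come from visits at which a subject leaves, or from extra visits arranged because of an adverse event. Those readings are more likely than most to be abnormal.

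Two consequences follow. First, a subject who leaves before day 71 can have the protocol-required exit ECG and laboratory tests done and still contribute no post-dose value to the laboratory and ECG summaries or shift tables. Second, the worst-grade LSR table and the treatment-emergent ECG table are defined per subject, but 7.9.2 has no exception for them. Two programmers could produce different tables from the same SAP. In one version an LSR maximum is understated, or an early leaver counts in the ECG denominator with no value to contribute.

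**Working it through.** The plan states no figure on this point, so there is none to reproduce. The check applies the 7.9.2 rules to each possible day of an ET visit.

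**Inputs.** Windows and exclusions are from SAP 7.9.2, with target days 8, 29, 57 and 85. Visit tolerances are from Protocol 8.3 to 8.6 (Week 1 ±2 days; Weeks 4 and 8 ±4 days). Assumption: the leaver attended every scheduled visit before the ET visit.

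**Coverage.** The windows meet at days 18/19, 42/43 and 70/71, so days 5 to 98 are covered without gaps.

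**Laboratory tests and ECGs at an ET visit, days 2 to 85 (84 days).**
- Days 2 to 4: before day 5, dropped (3 days).
- Days 5 to 70: mapped to Week 1, 4 or 8, where neither assessment is scheduled or tabulated, dropped (66 days).
- Days 71 to 85: mapped to Week 12, kept (15 days).
- Dropped: 3 + 66 = 69; 69/84 = 82%.

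SAP 7.9.8.5.1 gives ECG descriptive statistics by visit without naming the visits, but Week 12 is the only scheduled post-dose ECG and the shift tables name it.

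**LSR grades at an ET visit, days 2 to 85, leaving out the three scheduled visit days (84 − 3 = 81 days).** With earlier visits on target:
- Dropped: days 2–4, 9–18, 30–42 and 58–70 = 3 + 10 + 13 + 13 = 39; 39/81 = 48%.
- Kept: days 5–7, 19–28, 43–56 and 71–85 = 3 + 10 + 14 + 15 = 42.

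If earlier visits all fall at the early edge (days 6, 25, 53), 3 + 12 + 17 + 17 = 49 are dropped; 49/81 = 60%. At the late edge (days 10, 33, 61), 3 + 8 + 9 + 9 = 29 are dropped; 29/81 = 36%.

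**Unscheduled readings in a subject who attends every visit.** All windows are filled, so every unscheduled LSR grade is dropped from the by-visit table. Unscheduled ECGs and laboratory results are likewise dropped from the Week 12 tables.

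**The conflict, by illustration.** A subject has grade 1 erythema at Week 4 (day 29) and grade 2 at an ET visit on day 35. Day 35 maps to Week 4, which is filled. Under 7.9.2 the grade 2 is not analysed and the worst grade is 1; under 7.9.8.4 read alone it is 2. The same visit's ECG qualifies the subject for the treatment-emergent ECG table under 7.9.8.5.1, but 7.9.2 removes the value.

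**Number of subjects.** The documents give no dropout timing. If 5% to 15% of 700 left before day 71 with an ET visit (an assumption), 0.05 × 700 = 35 to 0.15 × 700 = 105 subjects would have no post-dose value in the Week 12 laboratory and ECG tables. Exits for intolerance may be far fewer. Protocol 1.2 reports that 7 of 420 subjects in the Phase 2 dose-ranging study stopped drug for an adverse event, 4 of them for treatment-related events. Scaled to 700, that is 7/420 × 700 ≈ 12 and 4/420 × 700 ≈ 7. That study enrolled adults only and used other strengths, so this is a rough guide.

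**The case against.** The strongest reply is that little of importance is lost. Mapping includes ET and unscheduled data by default: LSR grades in unfilled windows are tabulated, as are ET laboratory and ECG values on days 71 to 98 when no scheduled Week 12 data exist. Adverse event tables (SAP 7.9.8.2) use no visit mapping. Protocol 9.4.5 makes an LSR scored severe on a visit day an adverse event, and also any LSR experienced between visits. Protocol 9.4.4 does the same for clinically significant laboratory results. A grade 3 reaction at a day-35 exit would therefore appear in the adverse event tables and in the severe-LSR listing. All of this stands.

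It does not dispose of the point. A mild or moderate LSR seen on a visit day is not an adverse event under 9.4.5, so at an excluded visit it could survive only in a listing. Protocol 9.4.3 has no adverse event instruction for ECG findings like those for laboratory results and vital signs, although the general definition in 9.4.6 would still cover an untoward one. QTcF and laboratory shifts not recorded as adverse events have no other table. And a grade 3 that is tabulated as an adverse event but absent from the worst-grade table would leave the outputs in disagreement.

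It can also be said that 7.9.2 only assigns values to visits and was never meant to govern subject-level tables. That is possible. But the section speaks of analyses in general, sets them against listings, and makes an exception only for baseline values. Nor does Appendix 1's shared Week 12/ET column rescue early ET values, because 7.9.2 expressly maps them by day.

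**Conclusion.** The concern holds in a limited form. For laboratory tests and ECGs the loss follows directly from the text: ET values on days 5 to 70 are excluded from the laboratory and ECG summaries and shift tables. For the worst-grade LSR, overall LSR severity and treatment-emergent ECG tables, exclusion is the plain reading of 7.9.2 but is not stated expressly. There the fault is a conflict between sections that must be settled before programming.

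A reader might infer more than the documents support:

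- That ET and unscheduled readings vanish from every safety table. They do not: inclusion is the default, and adverse event tables are untouched.
- That excluded readings survive only in listings. That applies mainly to mild or moderate LSRs seen at an excluded visit, and to laboratory or ECG values not recorded as adverse events.
- That 82% or 48% of subjects or readings are affected. These are shares of possible visit days, and the LSR figure assumes earlier visits were attended on target. The number of subjects is unknown.
- That the comparison is biased toward active. That needs active to be less well tolerated than vehicle, which the documents do not show.

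The SAP should be changed: following it as written discards safety readings that the protocol requires sites to collect.

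**What to change.** 1. In SAP 7.9.2, limit the exclusions for filled windows, unplanned visits, days before 5 and days after 98 to by-visit safety tables.
2. In SAP 7.9.8.4 and 7.9.8.5.1, state that worst post-baseline LSR grade, overall LSR severity counts and treatment-emergent ECG abnormalities use all readings after the first dose (scheduled, unscheduled and ET) up to study exit. Give an explicit rule for readings after day 98, so that late off-treatment values are not brought in by default.
3. In SAP 7.9.8.3 and 7.9.8.5.1, add a Week 12-or-ET time point (last post-dose value) to the laboratory and ECG summaries and shift tables.

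No new data are needed. The cost is SAP wording and minor programming before unblinding, the limit Protocol 11.1 sets for finalising the SAP. A footnote should say that the worst-grade table need not equal the maximum of the by-visit tables.
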